Further, to obtain data on important potential confounders, specifically BMI, blood pressure, smoking, and laboratory measures such as HbA1c and eGFR, EMR databases will also be included in the study. Four regional EMR databases (Helsinki, Espoo, Vantaa, and Helsinki University Hospital [HUS] area), covering both primary and secondary care in the capital area of Finland, will be contacted separately to obtain access to their data. The data obtained from different data sources will be linked as described previously ([Section 8.4.2](#)).

Permissions to use the data may be received upon providing a research plan to the authorities responsible for the registers. The protocol is also subjected to relevant Ethical Committee's review and approval. The data permit processes and timelines for data permit granting by the authorities responsible for the registers vary between different registers and countries, as well as the requirements for the local research collaboration and the publication of results [[R15-4861](#)].

In Finland, all the data will be delivered to and analysed in the remote access server environment provided by the national permit authority Findata. The data holders will extract the relevant data and deliver it to Findata for pseudonymization. Before data delivery to the

Findata server environment, the data holders will collect and manage data according to their own standards. After the data is delivered to the Findata server environment by the data holders, [REDACTED] will process the data.

[REDACTED] will use the study identification numbers for data linkage on individual level. [REDACTED] will have access to pseudonymized raw data without PINs. Therefore, the researchers at [REDACTED] will have access to data where individuals cannot be directly identified.

In Finland, the full study data including follow-up period until the end of 2020 will be available in June 2022.

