8.9.2 Generalizability

In the current study three population-based data sources (CPRD GOLD, CPRD Aurum, and Swedish and Finnish national registries) will be used. CPRD GOLD provides data entered by primary care practitioners in a routine clinical care setting and covers approximately 8.8% of

the UK population and CPRD Aurum about 13% of England population. The patients are broadly representative of the UK population in terms of age, sex and ethnicity. In Sweden, the national registries cover practically all patients with T2D. In Finland, the coverage of the EMR data is approximately 26.7%, and study population is broadly generalizable. Therefore, the study results can be generalized to similar patients with T2D in other geographic settings, including most industrialized countries.

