Smoking status	Patient smoking status at index date. Evaluated at index date using closest value.	Time-fixed Categorical: Yes ³ No	UK: CPRD Sweden: NDR Finland: AvoHILMO, EMR databases
Alcohol use status	Patient alcohol use status at index date. Evaluated at index date using closest value.	Time-fixed Categorical: Yes No	UK: CPRD Sweden: NA Finland: NA
HbA1c value (in mmol/mol)	Time-dependent HbA1c measurement value in mmol/mol. Initialized at index using closest value to index date and updating from index date onwards.	Time-dependent Continuous Categorical: < 48 (6.5%) ≥48 (6.5 %)- <64 (8 %) ≥64 (8%)	UK: CPRD Sweden: NDR Finland: EMR databases

Proprietary confidential information © 2024 Boehringer Ingelheim International GmbH or one or more of its affiliated companies

Number of albuminuria tests	The number of albuminuria tests received by the patient prior to index date. Evaluate at index using all available history prior to index date.	Time-fixed Continuous	UK: CPRD Sweden: NDR Finland: EMR databases
-----------------------------	---	--------------------------	---

¹ The national patient register will be used if data on immigration/emigration are unavailable from the Total population register.

² Categories under-weight (<20), normal weight (20-24.9), overweight (25-29.9), and obese (>30) may be adjusted based on the observed distribution of the data.

³ In Sweden, a smoker is a patient smoking one or more cigarettes per day or a pipe daily or who had stopped smoking within the past 3 months. If data allows, categories current, never, past will be used.

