6.3. METHODS ADDRESSING BIAS

Potential biases will be addressed as follows:

- Selection bias and immortal time bias is addressed thru the study design. It include a new user cohort design, a selection of comparator drugs with the same indication and prescribed to patients with potentially similar T2D disease severity, and a definition of exposure and study entry based on information before or at index date.
- Channeling bias is addressed by using propensity score matching to construct balanced exposure groups. In addition, the year of the index date (date of first prescription of the study group) is used as an exact matching criteria.
- Bias due to definitions of exposure, definition of follow-up times and other relevant covariates will be addressed through sensitivity analyses.

Proprietary confidential information © 2024 Boehringer Ingelheim International GmbH or one or more of its affiliated companies

- Diagnostic bias will be evaluated and addressed in sensitivity analyses through consideration of the frequency of urine dipstick testing (as captured through albuminuria tests) and stage of cancer at the time of diagnosis (as more early-stage cancers in one group would be suggestive of diagnostic bias).

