Crude incidence rates	Using matched cohorts Country specific analysis (9 tables, 3 outcomes x 3 countries)	As treated exposure definition	Further outcomes- Table 9	Table 29
Hazard ratio estimates using adjusted model	Using matched cohorts (3 tables, 3 outcomes)	As treated exposure definition	Further outcomes- Table 9	Table 25
TNM staging at diagnosis	Using matched cohorts (9 tables, 3 outcomes x 3 countries)	As treated exposure definition	Further outcomes- Table 10	Table 21
Albuminuria tests each year	Using matched cohorts (3 tables, 3 countries)	As treated exposure definition	NA	Table 36
Sensitivity analysis:				
Extended latency period				
Hazard ratio estimates using adjusted model	Using matched cohorts Duration of latency period is extended to 12 months. (3 tables, 1 outcome x 3 countries)	As treated exposure definition	Urinary tract cancer as defined in Table 8	Table 25
Meta-analysis of adjusted HR estimates	Using adjusted HR estimates with 95% CIs from all study countries (1 figure, 1 outcome)	As treated exposure definition	Urinary tract cancer as defined in Table 8	Figure 8
Hazard ratio estimates using adjusted model	Using matched cohorts Discontinuation is 6 months after last day of medication or switch. (3 tables, 1 outcome x 3 countries)	As treated exposure definition	Urinary tract cancer as defined in Table 8	Table 25
Meta-analysis of adjusted HR estimates (discontinuation is 6 months after last day of medication or switch)	Using adjusted HR estimates with 95% CIs from all study countries (1 figure, 1 outcome)	As treated exposure definition	Urinary tract cancer as defined in Table 8	Figure 8

Analysis	Details	Exposure definition	Outcomes	Template
Sensitivity analysis: Inclusion of the Aurum CPRD database				
Description of patient baseline characteristics for the UK, stratified by CPRD database	CPRD specific analysis (1 table)	N/A	N/A	Table 37
Stratified incidence rates	Using UK matched cohorts (3 tables, 3 outcomes x 1 country)	As treated exposure definition	Main outcomes- Table 8	Table 38
Hazard ratio estimates using crude model after adding CPRD database as a stratification variable	Using UK matched cohorts (3 tables, 3 outcomes x 1 country)	As treated exposure definition	Main outcomes- Table 8	Table 39
Hazard ratio estimates using the base model after adding CPRD database as a stratification variable	Using matched cohorts Only for the UK (3 tables, 3 outcomes x 1 table)	As treated exposure definition	Main outcomes- Table 8	Table 40

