Table 36. Number of yearly albuminuria tests stratified by exposure group - [Study country]

	Empagliflozin	DPP-4 inhibitors
No. of tests		
0	N (x.xx%)	N (x.xx%)
1	N (x.xx%)	N (x.xx%)
2	N (x.xx%)	N (x.xx%)
More than 2	N (x.xx%)	N (x.xx%)
Range (min,max)	(min, max)	(min, max)
mean (± sd)	mean (± sd)	mean (± sd)
median (Q1,Q3)	median (Q1,Q3)	median (Q1,Q3)

Proprietary confidential information © 2024 Boehringer Ingelheim International GmbH or one or more of its affiliated companies

Table 37 Patients baseline characteristics in each of the study groups in the UK, stratified by CPRD database.

	GOLD		Aurum	
	Empagliflozin N =	DPP-4 inhibitors N =	Empagliflozin N =	DPP-4 inhibitors N =
Age at index (years)				
18-49	N (x.xx%)	N (x.xx%)	N (x.xx%)	N (x.xx%)
50-64	N (x.xx%)	N (x.xx%)	N (x.xx%)	N (x.xx%)
65-69	N (x.xx%)	N (x.xx%)	N (x.xx%)	N (x.xx%)
70-74	N (x.xx%)	N (x.xx%)	N (x.xx%)	N (x.xx%)
75-79	N (x.xx%)	N (x.xx%)	N (x.xx%)	N (x.xx%)
80-84	N (x.xx%)	N (x.xx%)	N (x.xx%)	N (x.xx%)
85 and over	N (x.xx%)	N (x.xx%)	N (x.xx%)	N (x.xx%)
Range (min,max)	(min, max)	(min, max)	(min, max)	(min, max)
mean (± sd)	mean (± sd)	mean (± sd)	mean (± sd)	mean (± sd)
median (Q1,Q3)	median (Q1,Q3)	median (Q1,Q3)	median (Q1,Q3)	median (Q1,Q3)
Sex				
Male	N (x.xx%)	N (x.xx%)	N (x.xx%)	N (x.xx%)
Female	N (x.xx%)	N (x.xx%)	N (x.xx%)	N (x.xx%)
Highest level of education				
Compulsory	N (x.xx%)	N (x.xx%)	N (x.xx%)	N (x.xx%)
Upper secondary	N (x.xx%)	N (x.xx%)	N (x.xx%)	N (x.xx%)
Post secondary	N (x.xx%)	N (x.xx%)	N (x.xx%)	N (x.xx%)
Disposable income, Individual				
< Q1	N (x.xx%)	N (x.xx%)	N (x.xx%)	N (x.xx%)
Q1 – Q2	N (x.xx%)	N (x.xx%)	N (x.xx%)	N (x.xx%)
Q2 – Q3	N (x.xx%)	N (x.xx%)	N (x.xx%)	N (x.xx%)
≥ Q3	N (x.xx%)	N (x.xx%)	N (x.xx%)	N (x.xx%)
Range (min,max)	(min, max)	(min, max)	(min, max)	(min, max)
mean (± sd)	mean (± sd)	mean (± sd)	mean (± sd)	mean (± sd)
median (Q1,Q3)	median (Q1,Q3)	median (Q1,Q3)	median (Q1,Q3)	median (Q1,Q3)
Disposable income, family				
< Q1	N (x.xx%)	N (x.xx%)	N (x.xx%)	N (x.xx%)
Q1 – Q2	N (x.xx%)	N (x.xx%)	N (x.xx%)	N (x.xx%)
Q2 – Q3	N (x.xx%)	N (x.xx%)	N (x.xx%)	N (x.xx%)
≥ Q3	N (x.xx%)	N (x.xx%)	N (x.xx%)	N (x.xx%)

Proprietary confidential information © 2024 Boehringer Ingelheim International GmbH or one or more of its affiliated companies

Range (min,max)	(min, max)	(min, max)	(min, max)	(min, max)
mean (± sd)	mean (± sd)	mean (± sd)	mean (± sd)	mean (± sd)
median (Q1,Q3)	median (Q1,Q3)	median (Q1,Q3)	median (Q1,Q3)	median (Q1,Q3)

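### Table 36, a check on diagnostic bias, counts yearly albuminuria tests in all matched Finnish patients although Finnish tests are visible only in capital-area records, and its shell has no covered denominator or person-time

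*SAP*

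**What the plan says.** SAP 6.3 states the purpose: "Diagnostic bias will be evaluated and addressed in sensitivity analyses through consideration of the frequency of urine dipstick testing", with albuminuria tests as the measure and stage at diagnosis as the companion check. The SAP 6.10 list of analyses (Table 16, sensitivity analysis on outcomes) gives the population for the yearly albuminuria table as "Using matched cohorts (3 tables, 3 countries", with the as-treated exposure definition. No restriction to patients with test data is stated.

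The shell in SAP Annex III is "Table 36. Number of yearly albuminuria tests stratified by exposure group - [Study country". For each drug it shows counts in rows 0, 1, 2 and more than 2, then range, mean and median. It has no row for patients whose tests cannot be seen and no person-years column. Table 21 (stage) has NA rows, and Tables 22 and 29 to 32 have person-years.

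The only visible data source for test counts is the baseline variable in SAP 5.3.1 (Table 11), defined as "The number of albuminuria tests received by the patient prior to index date", with source "UK: CPRD Sweden: NDR Finland: EMR databases". Protocol 8.4.3 describes the Finnish databases as "covering both primary and secondary care in the capital area of Finland". Protocol 8.9.2 says "In Finland, the coverage of the EMR data is approximately 26.7%, and study population is broadly generalizable".

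**The concern.** The table is meant to show whether a cancer excess on empagliflozin could come from more urine testing. That requires separating a patient who was observed and not tested from a patient whose tests cannot be seen. For most Finnish patients the visible plan gives no means of doing so. A count built from records returns 0 when there are no records, unless coverage is defined first.

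The yearly counts raise a second problem. As-treated follow-up ends 90 days after stopping or switching (SAP 5.1.3, Table 4), so many patients contribute part-years. Neither Table 16 nor the shell says how a part-year is counted.

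At stake is the reading of one of the two diagnostic-bias checks in Finland. No hazard ratio uses Table 36.

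**Working it through.** **Inputs.** Coverage c = 0.267 (Protocol 8.9.2), assumed here to apply to the matched cohort. Finland: 18,269 empagliflozin initiators matched 1:2 (Protocol 8.5), hence 36,538 comparators. The yearly Finnish counts in Protocol Table 6 (0, 91, 2,201, 3,725, 4,293, 5,182, 2,777) do sum to 18,269. The 26.7% is a bare input and cannot be rebuilt. The documents give no testing rates, so those below are assumptions.

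**If uncovered patients are counted as 0, with equal coverage by arm.** Table mean = c × true mean.
- The mean is 1 − 0.267 = 73.3% below the true one.
- True 1.2 v 1.0 tests per year becomes 0.320 v 0.267. The difference falls from 0.20 to 0.053; the ratio stays 1.20.
- True 1.5 v 1.0 becomes 0.401 v 0.267. The difference falls from 0.50 to 0.134; the ratio stays 1.50.
- At least 73.3% of each arm is in the 0 row, so both medians are 0. With Poisson testing at 1.0 per year the row holds 0.733 + 0.267 × e^−1 = 83%, against 37% among covered patients.
- Poisson variance in the table is c(λ + λ²) − (cλ)²: 0.463 at λ = 1.0 and 0.602 at λ = 1.2. The standardised difference is 0.053/√[(0.463 + 0.602)/2] = 0.07, against 0.2/√1.1 = 0.19 among covered patients.
- Share with at least one test, 66% v 60%: shown as 17.6% v 16.0%, and the standardised difference falls from 12.5% to 4.3%.

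**If coverage differs by arm.** Table ratio = (c_E × m_E)/(c_D × m_D). With true means of 1.2 and 1.0:

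| Coverage, empagliflozin v DPP-4 | Table means | Ratio (true 1.20) |
|---|---|---|
| 26.7% v 26.7% | 0.320 v 0.267 | 1.20 |
| 22% v 26.7% | 0.264 v 0.267 | 0.99 |
| 30% v 26.7% | 0.360 v 0.267 | 1.35 |

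The unequal values are illustrations. Matching uses the index-date window, metformin status and the propensity score (SAP 6.5.2), and region is not a Table 11 covariate, so nothing forces coverage to be equal.

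**Part-observed years.** Suppose each calendar year touched counts as one year, start dates are uniform within the year, and follow-up length does not depend on start date. Mean follow-up of m years then touches 1 + m calendar years on average, so the observed share is m/(1 + m). For m = 2.4 this is 0.71; for m = 1.5 it is 0.60. With equal testing, an arm followed 1.5 years would show 0.60/0.71 = 0.85 of the count of an arm followed 2.4 years. With the 2.2 and 2.4 years that Protocol 8.5 expects for different countries, used here only as a mild contrast between arms, the figure is 0.69/0.71 = 0.97. The distortion between arms arises only if follow-up differs by arm.

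**With the restriction.** About 0.267 × 18,269 = 4,878 empagliflozin and 9,756 DPP-4 patients remain, and the true means and differences are recovered. For 63% v 60% with at least one test, power of a two-sided 5% comparison is 94.0% in covered patients, against 66.7% in all matched patients with zeros filled in.

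**The case against.** No visible text says that uncovered patients are counted as 0. SAP section 9 applies its absence-means-no-event rule to medical history conditions. It expects missing values in biological measurements and provides a missing category; above 50% missing, removal is considered. If uncovered patients were treated as missing, the shortfall would be nil. The lack of a missing row proves little, since the Table 17 and 18 shells also omit one for HbA1c and eGFR. SAP 6.8 and 6.9 and Protocol 8.7.2 are not in the public copy and may define the population and the year rule. A yearly count might also be annualised.

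Even with zeros filled in, equal coverage leaves the ratio at 1.20. The difference of 0.053 has a standard error of √(0.602/18,269 + 0.463/36,538) = 0.0068, so z is about 8. UK and Swedish tables, 49,221 of 67,490 expected initiators (73%), are untouched by Finnish coverage.

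Most of this stands and limits the size of the point. Section 9 is still not a repair. Without a coverage rule based on residence, a Finnish patient with no test record cannot be sorted into covered and untested or not covered. The removal option names the propensity score, Cox and nested case-control uses, and applying it here would drop the Finnish check. SAP section 10 checks output against the shells, so the shell matters.

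**Conclusion.** The point holds as a weakness in the design of Table 36, worth a cheap improvement. The visible plan tabulates integer yearly counts in all matched Finnish patients when tests can be seen in only about 26.7%, with neither a covered denominator nor person-time.

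The size is conditional. If uncovered patients enter as 0 and 26.7% applies to the cohort, Finnish means and absolute differences are about 27% of their true size and medians are 0 in both arms. The ratio is correct under equal coverage and can move either way otherwise.

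A reader might infer that Finnish testing rates will be 73% too low, that a real difference between the drugs will be hidden, or that part-years understate testing by a fixed amount in every country. The documents do not support these as facts. Zero-coding is inferred, the base of the 26.7% is unstated, the ratio survives equal coverage, and no part-year rule is visible. Any rule in the redacted section should be checked first.

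**What to change.** 1. **Finland.** In Table 36 and its Table 16 row, restrict to matched patients resident in the four catchment areas and to person-time with record coverage. Protocol 8.4.3 already obtains residence from the Population register centre. Show the covered and uncovered numbers by arm, with uncovered patients outside the 0 row.
2. **All countries.** Beside the count rows, report tests per as-treated person-year by arm with 95% CI, and a rate ratio from Poisson regression with log person-time as offset.
3. **Baseline.** Treat the Finnish Table 11 test count as unobserved, not zero, outside coverage. It is a propensity-score candidate and is judged by the 10% balance rule in SAP 6.6.2; under zero-coding, the standardised difference of 0.19 in the example above would appear as 0.07 and pass.

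This changes one shell and a few lines of SAP text and needs no new data. The Finnish check would then rest on about a quarter of Finnish patients, the only ones whose tests can be seen.

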Annex IV

List of drug dosages for empagliflozin, DPP-4 inhibitors and metformin

List of drug dosages extracted from registries in Finland and Sweden:

Annex 4 - List of
drug dosages.xlsx
